7.3.2. Blinding

The PI, study staff, and participants will be blinded as to receipt of active vaccines or placebo but the PI and study staff will not be blinded to group allocation as it pertains to the inclusion of ALFQ. Since the vaccines and placebos are not identical in appearance, to preserve blinding the material inside the syringe will be masked by the pharmacist. In addition, the pharmacy staff preparing the vaccine syringes will not be involved in the clinical assessment of participants and will be instructed not to comment on the appearance of experimental agent to study staff. For all participants, the volume of injections will be consistent.

Pharmacy staff will be trained in GCP and instructed not to discuss the vaccine randomization lists, codes, or participant assignments with study personnel. Pharmacy staff will be required to sign a confidentiality agreement and will be the only person(s) on site who will know the randomization assignment. The randomization assignment will not appear on any label or source document leaving the pharmacy. Samples will be labeled on site using labels containing participant study numbers, protocol number and visit number. The samples will be accompanied by a specimen tracking form that records the study number, date and time of sample collection.

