4. INVESTIGATIONAL PLAN

4.1. Overall Study Design and Plan

This is a Phase I randomized, double-blind, placebo-controlled clinical trial to define the safety and immunogenicity of IHV01/A244 with and without ALFQ at a full dose and at a fractional dose in a late boost setting for participants who had previously received the AIDSVAX®B/E with or without ALVAC in RV306. Participants will be randomized to receive 2 intramuscular (IM) injections, either IHV01/A244 (target of n=64 total, with n=16 per study arm) or saline placebo (target of n=16 total, with n=4 per study arm), into the same quadriceps muscle at Day 0. Half of the IHV01/A244 recipients will receive the full IHV01 (FLSC) dose (Groups 1 and 3) while the other half (Groups 2 and 4) will receive a fractional dose of each vaccine, which is one fifth of the standard dose. Groups 3 and 4 will also receive ALFQ. Enrollment will be sequential, with Groups 1 and 2 accruing first with a 2:2:1 ratio of full dose to fractional dose to placebo, followed by enrollment into Groups 3 and 4 with the same targeted allocation ratios. After the first 8 participants are enrolled across Groups 1 and 2, the Safety Monitoring Committee (SMC) will review 7 days of safety data from these participants to determine whether enrollment can continue. Enrollment into Groups 1 and 2 will continue unrestricted after any safety concerns raised by the SMC are addressed and the Sponsor gives their approval for the continuation of enrollment. Enrollment into Groups 3 and 4 will commence after enrollment into Groups 1 and 2 has been completed, the SMC has reviewed 7 days of safety data from all Group 1 and Group 2 participants, and the Sponsor gives their approval. Enrollment into Groups 3 and 4 will follow a similar approach with an SMC review of 7 days of safety data from the first 8 participants enrolled across both groups, and Sponsor approval before enrollment can continue unrestricted in Groups 3 and 4.

Participants will receive 2 IM injections, either IHV01/A244 (n=64) or saline placebo (n=16) at Day 0, and return for follow up at 1, 7, 14, 168, and 336 days after vaccination (protocol version 5.0, section 7.2). Figure 1 gives a schematic of the study design, with the RV306 groups shown on the left and the RV546 groups on the right.

Figure 1: Study Schematic

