4.2. Discussion of Study Design, Including the Choice of Control Groups

This study uses a factorial, placebo concurrent control design to assess the safety and immunogenicity of varying doses of the same vaccine with or without the ALFQ adjuvant. This is a Phase I study with a primary objective of characterizing the safety of the study vaccination, so saline placebo was chosen as the control.

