4.4.2. Allocation of Participants to Study Arms (Randomization)

A randomization schedule will be centrally generated by the protocol statistician. The study will recruit approximately equal numbers of males and females, but formal targets for randomization will not be established. **Table 1** shows the planned vaccination group allocation.

Randomization is stratified by clinical site, with a separate list generated for each site. Blocks will be used within each stratum to maintain balance in assignments over time.

Randomized participants who withdraw before receiving study vaccination will be replaced, with the replacement participant receiving the same assignment.

After the protocol amendment to reduce the total sample size, implemented in version 5.0 of the protocol, a new set of assignments was generated for Groups 3 and 4 based on the updated allocation ratios. Randomization into Groups 1 and 2 was stopped prior to the initial target, to approximately maintain these new group sizes.

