4.5.5. Blinding

The PI, study staff, and participants will be blinded as to receipt of active vaccines or placebo but will not be blinded to group allocation as it pertains to the inclusion of ALFQ, due to the planned sequential enrollment. Since the vaccines and placebos are not identical in appearance, to preserve blinding the material inside the syringe will be masked by the pharmacist. In addition, the pharmacy staff preparing the vaccine syringes will not be involved in the clinical assessment of participants and will be instructed not to comment on the appearance of experimental agent to study staff. For all participants, the volume of injection will be consistent.

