7.1. Primary Safety Analysis

7.1.1. Unsolicited Adverse Events

Unsolicited AEs will be listed and summarized by MedDRA system order class (SOC) and preferred term (PT) for each vaccination group. These will be described overall and within 28 days post-vaccination. A participant will be counted only once per PT per reporting period. SAEs, unexpected AEs, and AESIs will be summarized and listed. The number and percentage of participants reporting each PT, along with the associated 95% exact Clopper-Pearson CI for the underlying probability of the event, will be presented.

The likelihood of reporting AEs, SAEs, and AESIs will be compared between collapsed groups (Groups 1+2 vs. Groups 3+4 to assess ALFQ safety, Groups 1+3 vs. Groups 2+4 to assess vaccine dose) via exact binomial tests. If computational challenges arise, Chi-squared tests may be used instead. Calculated confidence intervals will be used to compare pairs of individual vaccination groups, instead of formal hypothesis testing; when CIs for the same event in two groups do not overlap, this corresponds to a p-value of less than 0.05 for the analogous exact binomial test.

Unsolicited AEs will also be tabulated by investigator-determined relationship to investigational product and severity for each vaccination group.

Incident HIV infections, as diagnosed by the algorithm in Section 11.1.4.4 of the protocol, will be presented in a listing.

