8. IMMUNOGENICITY EVALUATION

8.1. Primary Immunogenicity Analysis

The primary immunogenicity endpoint is the magnitude of plasma IgG (antigen-specific) responses as measured by the endpoint titer, the same variable assessed in RV306. GMTs will be calculated for each group at each visit and the per-participant peak across all visits, along with 95% CIs (exponentiating the CI limits for the log GMT based on the normal distribution). Hypothesis testing is planned for targeted time points; this will be performed in order to aid in interpretation by helping to determine immune responses for potential further examination in future studies. First, group GMTs will be compared across all vaccination groups via ANOVA (null hypothesis that all groups share the same GMT) at the 5%-level, and if that is found to be significant, pairwise comparisons via 2-sided t-tests and the Bonferroni-Holm step-down procedure will be made and a 1% significance threshold will be applied. The two collapsed comparisons will be via 2-sided t-tests of log-GMTs at the $\alpha=0.025$ -level. If the data appear especially non-normal, nonparametric testing will be considered instead.

The reverse cumulative distribution (RCD) of titers (with endpoint titer on the x-axis and the proportion of participants with at least that titer on the y-axis) at each visit will be shown by vaccination group, separately for each antigen.

Seroconversion or seropositivity post-vaccination will be defined based on criteria given by the performing lab, and the number and percent of participants in each group achieving seroconversion/seropositivity at each visit will be presented along with the associated exact 95% Clopper-Pearson CI. The same group comparisons will be performed, via exact binomial tests and the same handling of significance and multiplicity.

Immune response over time (durability) will be assessed by the positive incremental area under the curve (AUC) based on a graph with log endpoint titer on the y-axis and visit day on the x-axis. For comparability between participants with different numbers of samples (visits) available, these values will be scaled by the week of the last available sample. If no sample is available for visits other than the first and last, no explicit imputation will be done, and the AUC will be calculated based on available samples. Log AUC will be analyzed similarly to the visit-by-visit titers.

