8.2. Additional Immunogenicity Analyses

Further immunogenicity analyses (see Section 3.2.2 for planned sets of assays) will be considered exploratory for testing purposes (see Section 5.8 for how significance and multiplicity will be handled), but they will otherwise follow a similar process as the primary immunogenicity analysis. For assays that are not conducted via titer experiments, the analysis values will be handled as log GMTs are, after appropriate transformation of the data to be

approximately normal when necessary; instead of RCD curves, boxplots will show the assay values for each group, by visit.

The kinetics of log IgG titers over time will be assessed via generalized estimating equations (GEE) models, with the immune response appropriately-transformed to assume normally-distributed error terms and RV546 vaccine dosage, adjuvant, study day, and all 2- and 3-way interactions included as covariates. These covariates will be assessed for significance at the 1%-level, and any findings will be considered hypothesis-generating. An unstructured working covariance matrix will be preferred, but other choices may be necessary due to computational challenges or poor model fit. These details will be described in the final report. Similar models may be fit for other assays, and these would also be considered exploratory.

To assess the relationship between possible confounders and the appropriately-transformed titers at the primary endpoint time point, a linear regression model will be fit as well, adjusting for vaccination group, age, sex, RV306 vaccination group, and time between final RV306 vaccination and RV546 vaccination. Covariates will be assessed for significance at the 1%-level, and again findings will be considered hypothesis-generating. Similar models may be fit for other assays also.

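### ALFQ is assigned by enrolment stage, not by randomisation, yet the SAP tests it like the randomised dose contrast, without a caveat or an adequately adjusted estimate

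*SAP*

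**What the plan says.** **Allocation.** SAP 4.1 has Groups 1 and 2 (no ALFQ) enrolled first, with full dose, fractional dose and placebo in a 2:2:1 ratio. Then "Enrollment into Groups 3 and 4 will commence after enrollment into Groups 1 and 2 has been completed", subject to safety review and sponsor approval. SAP 4.4.2 adds that after the sample-size amendment "a new set of assignments was generated for Groups 3 and 4". Randomisation is stratified by site only.

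**Design label.** SAP 4.2: "This study uses a factorial, placebo concurrent control design".

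**Blinding.** Protocol 7.3.2: "the PI and study staff will not be blinded to group allocation as it pertains to the inclusion of ALFQ". SAP 4.5.5 says this of participants as well as the PI and staff: "but will not be blinded to group allocation as it pertains to the inclusion of ALFQ, due to the planned sequential enrollment". Loss of blinding is the only consequence of staging that either document discusses.

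**Tests.** SAP 7.1.1 compares adverse events between collapsed groups ("Groups 1+2 vs. Groups 3+4 to assess ALFQ safety, Groups 1+3 vs. Groups 2+4 to assess vaccine dose) via exact binomial tests"). SAP 8.1 says of plasma IgG: "The two collapsed comparisons will be via 2-sided t-tests of log-GMTs", each at 0.025. Log AUC is analysed similarly.

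**Models.** The exploratory regression in SAP 8.2 is described as "adjusting for vaccination group, age, sex, RV306 vaccination group, and time between final RV306 vaccination and RV546 vaccination". Its shell (Table 36) has no Day 0 titer row. The exploratory GEE (Table 35) has Day 0 as the reference study day but no RV306 interval.

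**Baseline tables.** SAP 4.9 and Tables 8 and 9 cover age, sex, education, occupation and BMI. RV306 regimen and interval are absent.

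**The concern.** The two collapsed contrasts have different standing. Dose is randomised within each stage. ALFQ is not randomised: every active participant in stage 2 receives it and none in stage 1 does. Any difference between stages in who enrolled, in time since RV306 or in how events were elicited goes straight into the ALFQ estimate. A reader of Tables 15, 31 and 34 would give both p-values equal weight.

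The omission is at odds with the SAP's own reasoning. SAP 8.2 treats RV306 group and interval as possible confounders, and SAP 5.7 checks baseline balance between sites for that reason. Their balance between the ALFQ and non-ALFQ cohorts is never tabulated.

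Protocol 12.2.3 names with versus without ALFQ as a key safety comparison. Protocol 5.5.3 intends the ALFQ safety data to support use with other vaccine candidates. For titers, interval is a credible route for bias: the protocol introduction reports higher peak plasma IgG in RV306 when the boost came at month 15 or 18 rather than month 12.

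**Working it through.** **1. The plan's own figure.** SAP Table 4 gives detectable differences of 0.71/0.76/0.82 SD at 80/85/90% power for 32 vs 32, two-sided 0.05. A noncentral t with df = 62 and noncentrality d/√(1/32 + 1/32) = 4d gives 0.711/0.761/0.823, so the table reproduces. At the 0.025 level the SAP actually uses, the 80% figure is 0.79 SD.

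**2. Effect of a stage shift.** Put an assumed stage difference δ (in titer SDs) into the same formula, with no ALFQ effect and two-sided 0.025:

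| δ | 0 | 0.1 | 0.2 | 0.3 | 0.5 |
|---|---|---|---|---|---|
| Rejection | 2.5% | 3.6% | 7.4% | 14.4% | 38.9% |

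At the SAP's stated SD of 0.5 to 1.0 log units, 0.3 SD is 0.15 to 0.30 log units.

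**3. How far apart the stages may be.** The protocol synopsis estimates first enrolment in June 2021 and last completion in December 2023; follow-up is 336 days.
- Longest window: 1 June 2021 to 31 December 2023 is 943 days; 943 − 336 = 607 days, or 19.9 months.
- Shortest window: 30 June 2021 to 1 December 2023 is 884 days; 884 − 336 = 548 days, or 18.0 months.
- Let stage 1 fill [0, a] and stage 2 fill [b, 1] of the window, with even enrolment. The stage means differ by (1 + b − a)/2, which is at least 1/2 because b ≥ a. The gap is therefore at least 9 to 10 months.

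If RV306 completion date does not differ by stage, this is also the shift in RV306 interval.

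**4. From interval to titer.** Shift = correlation × 9 / (within-stage SD of interval in months). Correlation and SD are assumptions. Cells give shift and rejection at 0.025:

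| Correlation | SD 6 | SD 12 | SD 24 |
|---|---|---|---|
| 0.1 | 0.15; about 5% | 0.075; 3.1% | 0.04; 2.7% |
| 0.2 | 0.30; 14.4% | 0.15; about 5% | 0.075; 3.1% |
| 0.3 | 0.45; 31.6% | 0.225; 8.8% | 0.11; 4.0% |

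**5. Safety.** Assume a 40% event rate and extra reporting in stage 2 unrelated to ALFQ, 32 vs 32, with Fisher's exact test at 5% taken as the SAP's exact test. With 0/5/10/15/20 extra percentage points, rejection is 3.0%/4.5%/9.1%/17.5%/about 30%. This applies to unsolicited events or systemic symptoms. It does not apply to local reactions, which protocol 5.5.3 reports as near-universal with ALFQ.

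**6. What adjustment costs and recovers.** Two equal stages 9 months apart have a between-stage SD of 4.5. The stage-interval correlation is r = 4.5/√(SD² + 4.5²), and the SE is multiplied by 1/√(1 − r²):

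| Interval SD (months) | r | SE factor | Detectable, 0.025, 80% power |
|---|---|---|---|
| 3 | 0.83 | 1.80 | 1.42 SD |
| 6 | 0.60 | 1.25 | 0.98 SD |
| 12 | 0.35 | 1.07 | 0.84 SD |

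Day 0 titer recovers √(1 − ρ²): a factor of 0.95 at ρ = 0.3 and 0.87 at ρ = 0.5.

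A simulation (4,000 runs, linear model, gap 9, interval correlation 0.2, Day 0 correlation 0.5, no ALFQ effect) gave these results:
- Interval SD 6: rejection 14.6% unadjusted and about 2.2% adjusted; mean SE 0.249 and 0.269.
- Interval SD 12: about 4% to 5% and about 2.2% to 2.6%; mean SE about 0.249 and 0.228.
- Adding age, sex and an RV306 group that overlaps with interval kept adjusted rejection at about 2.2% to 2.4%.

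**7. Can the placebo arm detect a shift?** The target is about 8 per stage. At 8 vs 8 and 5%, power against 0.1/0.2/0.3/0.5 SD is 5.4%/6.6%/8.7%/15.4%, so it cannot.

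**The case against.** The strongest case is that most of this is disclosed or partly handled in a study that calls itself exploratory.
- Staged enrolment is stated openly, and no decision rule depends on the ALFQ p-value.
- Vaccination group identifies stage among active recipients, so Tables 8, 9 and 32 already allow demographics and Day 0 titer to be compared by stage.
- The SAP 8.2 regression contains group and interval, so an interval-adjusted ALFQ contrast can be derived from it. The GEE gives an ALFQ contrast relative to Day 0.
- The incremental AUC presumably subtracts Day 0 already, so the lack of a model with both covariates matters mainly for visit-wise titers.
- The size rests on stacked assumptions. The 31.6% pairs the most adverse values, and at an interval SD of 24 months rejection stays between 2.7% and 4.0%. The RV306 finding concerns the interval from priming to boost, not time since a last dose.
- Adjustment is least precise when interval tracks stage closely, and it does nothing for safety, the primary objective.

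All of this limits the weight and is accepted. It does not remove the point. The general exploratory wording covers both contrasts alike and never says that only one is randomised. The regression is not named as a check on the ALFQ test, and its time point is not defined. RV306 balance between cohorts is not shown anywhere.

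**Conclusion.** The concern holds. Among active recipients ALFQ and enrolment stage cannot be separated, and the SAP tests ALFQ as though it had been randomised. No caveat distinguishes it from the dose contrast, the RV306 variables are not tabulated by group, and no model holds both Day 0 titer and RV306 interval. The dose contrast is unaffected.

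The size is conditional. A stage shift of 0.2 to 0.3 SD takes the nominal 2.5% to 7.4% to 14.4%; the interval scenarios run from 2.7% to 31.6%. These rest on planning dates, even enrolment and assumed correlations, SDs and reporting differences. They are not estimates of bias in this trial. The change should be made, although no stated decision turns on it.

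**What to change.** 1. **Caveat.** Add one sentence to each of SAP 4.2, 7.1 and 8.1. It should say that the ALFQ comparison is between sequentially enrolled, non-randomised cohorts, that staff know which cohort is the ALFQ cohort, that its p-values are read accordingly, and that dose is randomised within stage. Align SAP 4.5.5 with protocol 7.3.2 on whether participants also know.
2. **Baseline tables.** Add RV306 group to Table 8 and time since final RV306 vaccination to Table 9.
3. **Supplementary estimate, primary plasma IgG only.** Keep the planned t-tests. Beside Tables 31 and 34, report the ALFQ difference with a 95% CI from the SAP 8.2 regression with Day 0 log titer added. Fit it in active recipients, so that unboosted placebo participants do not set the interval slope, and take the ALFQ contrast as a linear combination of the group coefficients. For the incremental AUC, adjust for interval without Day 0. Name the time points, say that the intervals are not read as tests, and state the precision loss if interval tracks stage.
4. **Optional.** Describe placebo by stage without a drift test, stating that it is too small to detect a plausible shift and cannot show an interval effect on boost response.

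**Cost.** Three sentences, two table entries and about 12 to 20 estimates: 4 named antigens × (AUC plus 2 or 3 post-baseline visits, with or without peak), so 4 × 3 to 4 × 5. The data are already needed for SAP 8.2, and the protocol's t-test stays. Adjustment cannot remove unmeasured stage differences or reporting bias in safety; there only the caveat applies.

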Study arms are given below in Table 1. For analysis purposes, participants will be grouped by vaccination regimen received, so placebo participants will be considered the fifth Vaccination Group.

Table 1: Study Arms

Group #	Intervention	Control
Group 1	16 Full IHV01/A244	4 placebo
Group 2	16 Fractional IHV01/A244	4 placebo
Group 3	16 Full IHV01/A244 + ALFQ	4 placebo
Group 4	16 Fractional IHV01/A244 + ALFQ	4 placebo

The schedule of events is given in Table 2 below, for reference.

Table 2: Schedule of Events

Visit	S1	1	2	3	4	5	6 (Exit)	7
Visit Day	-45 to -16	0	1	7	14	168	336	Post Database Lock
Visit Week		0	1	1	2	24	48	
Visit Month		0			0.5	6	12	
Visit Window			+2d	-/+2d	-2/+3d	-/+7d	-/+7d	
Clinical								
Informed Consent (Main, Storage/Future Use, Genetic, and Optional Procedures)	X							Final Results and Unblinding ⁵
Test of Understanding	X							
Enrollment and Randomization		X						
Vaccination		X						
Vital Signs ⁸ and Physical exam ¹	X	X		X	X	X	X	
Medical History & Concomitant Medications	X	X		X	X	X	X	
Adverse Event Documentation (AE, SAE, AESI)		X	X	X	X	X	X	
Diary Card		X	X	X				
HIV Risk Assessment/Risk Counseling	X	X			X	X	X	
Pregnancy Test & Pre/Post Counseling	X	X			X	X	X	
Urinalysis (blood, protein and glucose)	X	X	X	X	X	X	X	
CBC w/ diff & CD4	2	2	2	2	2	2	2	
Creatinine, ALT/AST	3.5			3.5	3.5	3.5	3.5	
Syphilis and Hepatitis B Serology	3.5							
HIV Testing & Pre/Post Counseling	6				6	6	6	
Optional Procedures								
Mucosal Secretions ^{2,7} ; Plasma LH and FSH (cervical secretions only)		X			X	X	X	
STI Testing ⁷	X							
Vaginal ^{2,7} and/or rectal ^{3,7} and/or penile ⁷ swab for microbiome and proteome		X			X	X	X	
Endocervical Cytobrush/swab ^{2,7}		X			X	X	X	
Pap Smear, if none available in last two years ⁷	X							

Visit	S1	1	2	3	4	5	6 (Exit)	7
Visit Day	-45 to -16	0	1	7	14	168	336	Post Database Lock
Visit Week		0	1	1	2	24	48	
Visit Month		0			0.5	6	12	
Visit Window			+2d	-/+2d	-2/+3d	-/+7d	-/+7d	
Sigmoid Biopsy ^{3,7}					X			
Lymph Node Biopsy					X			
Leukapheresis ⁴					X (10ml)			
Safety Tests for Biopsy or Leukapheresis (up to max possible volume) ¹⁰					20			
Research								
HIV Binding Antibody		SP			SP	SP	SP	
HIV Neutralizing Antibody Assays		6			6	6	6	
Functional Antibody Assays		SP			SP	SP	SP	
B-Cell Analysis ⁶		30		30	30	30	30	
Multiparameter Flow Cytometry		20			20	20	20	
Innate Cell Analysis		20	20	20	20	20	20	
Transcriptomics		20	20	20	20	20	20	
Additional Immunogenicity Testing ⁶		30		30	30	30	30	

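### Each vaccine group is compared with a placebo pool of which half, by target, was randomised in the other enrolment stage; the plan has no stage-wise display, concurrent supportive contrast or stratified all-active test

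*SAP*

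**What the plan says.** SAP 4.1 sets the targets as "either IHV01/A244 (target of n=64 total, with n=16 per study arm") and "saline placebo (target of n=16 total, with n=4 per study arm"). Enrolment is in two steps, "with Groups 1 and 2 accruing first with a 2:2:1 ratio of full dose to fractional dose to placebo" and then "followed by enrollment into Groups 3 and 4 with the same targeted allocation ratios". The steps do not overlap: "Enrollment into Groups 3 and 4 will commence after enrollment into Groups 1 and 2 has been completed", with a safety review and sponsor approval in between.

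For analysis, the same section merges the controls: "For analysis purposes, participants will be grouped by vaccination regimen received, so placebo participants will be considered the fifth Vaccination Group". SAP 6.2 repeats the pooling for disposition. SAP 8.1 compares the five groups by ANOVA and then pairwise. Table shells 30, 33 and 38 list each vaccine group against the single placebo group, and the safety shells have one placebo column. Enrolment stage appears in none of these analyses.

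SAP 4.2 describes the design thus: "This study uses a factorial, placebo concurrent control design to assess the safety and immunogenicity". Protocol 12.1 also lists one placebo group of 16 and says that it serves mainly for blinding. Protocol 12.2.4 names all active versus placebo as a comparison of interest, and SAP Table 4 gives its detectable difference.

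**The concern.** Randomisation supplies a concurrent control within each stage. The pooled analysis uses only part of that protection, because half of each vaccine group's comparator was recruited and vaccinated in a different period.

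The documents give reasons why the stages could differ:

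- Calendar time differs, and with it, in general, the interval since the last RV306 dose. SAP 8.2 treats that interval as a possible confounder.
- Staff know whether ALFQ is in use (Protocol 7.3.2), and SAP 4.5.5 is worded so that participants may know too. Solicited reactions are largely self-reported on diary cards.

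If a stage difference exists, the individual vaccine-versus-placebo estimates absorb part of it, and the pooled placebo rate need not describe the background of either stage.

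**Working it through.** **Inputs.** From SAP 4.1 and its Table 1: 16 vaccine recipients per group, 4 placebo recipients per group, allocation 2:2:1, so each stage has 16 + 16 vaccine and 8 placebo recipients. From SAP Table 4: two-sided 2-sample t-test at 0.05. The stage shift d, in SD units, is assumed.

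**1. The plan's own figures.** Exact noncentral-t power at 80% gives 0.793 SD (64 vs 16), 0.711 SD (32 vs 32) and 1.024 SD (16 vs 16). SAP Table 4 has 0.79, 0.71 and 1.02, so it is reproduced.

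**2. Non-concurrent share.** For any vaccine group this is 8/16 = 50% by target.

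**3. Bias of an individual contrast.** Let stage 2 lie d above stage 1, with no vaccine effect. The pooled placebo mean is (8 × 0 + 8 × d)/16 = d/2.

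- Groups 1 and 2: 0 − d/2 = −d/2.
- Groups 3 and 4: d − d/2 = +d/2.

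At d = 0.5 the bias is 0.25 SD. With the log-titer SD of 0.5 to 1.0 in SAP 4.4.1, that is 0.125 to 0.25 log units.

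**4. Error rate of individual contrasts** (simulation, no vaccine effect, 8 + 8 placebo; 40,000 to 50,000 runs per shift). The planned procedure is an ANOVA at 5%, then Holm over 10 pairs. SAP 8.1 gives a 1% threshold for the pairwise step and SAP 5.8 gives 5%, so both are shown.

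| d (assumed) | Plain 5% t-test | Planned, 1% threshold | Planned, 5% threshold |
|---|---|---|---|
| 0 | 5% | 0.1% | 0.4% |
| 0.25 | 6% | 0.2% | 0.6–0.7% |
| 0.5 | 10% | 0.4% | 1.5–1.6% |
| 1.0 | 24% | 1.7–1.8% | 6.4–6.5% |

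The last two columns are rates per vaccine–placebo pair. The chance of at least one false vaccine–placebo finding at d = 0.5 is about 1.5% (1% threshold) or 5 to 6% (5% threshold).

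**5. All active versus placebo.** Half of each side comes from each stage, so the bias is d/2 − d/2 = 0. The unstratified test still counts the stage difference as residual variance, about 1 + d²/4. At d = 1 this is 1.25, so the estimated SE is too large by √1.25 = 1.118. The effective critical value is 1.96 × 1.118 = 2.19, which a standard normal exceeds in absolute value 2.85% of the time. Simulation gives about 2.9%. Power at 0.79 SD falls from 80% to about 73% (72 to 73% in simulation). Stratifying by stage restores 5% and 80%.

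**6. Cost of stratifying that test.**

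- Unstratified SE: √(1/64 + 1/16) = 0.28 SD.
- Stratified SE: ½ × √(2 × (1/32 + 1/8)) = 0.28 SD.

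**7. Cost of a concurrent contrast.**

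- SE rises from √(1/16 + 1/16) = 0.354 SD to √(1/16 + 1/8) = 0.433 SD.
- The detectable difference at 80% power rises from 1.02 to 1.27 SD, and power at 1.02 SD falls from 80% to 61%.
- The zero-event upper 95% limit for 8 people is 1 − 0.025^(1/8) = 36.9%, against 1 − 0.025^(1/16) = 20.6% for 16.

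**8. A stage term in the five-group ANOVA instead.** The SE for Group 1 versus Group 3 rises from 0.354 to 0.612 SD, because Groups 1–2 and Groups 3–4 are then linked only through the placebo recipients.

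**The case against.** The strongest reply is that placebo plays a minor part. The trial is Phase I and descriptive, and the protocol itself forms one placebo group, mainly for blinding. The formal safety tests in SAP 7.1.1 compare collapsed vaccine groups and do not use placebo. The pairwise immunogenicity tests are strictly gated. The exploratory regression in SAP 8.2 adjusts for time since RV306, and if the incremental AUC is measured from baseline, a constant level shift largely drops out of it.

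Much of this stands. It limits the size of the problem and argues against replacing the main test. It does not remove the problem. The gate controls false findings but not the d/2 bias in the estimate, and it protects less once a real vaccine effect makes the ANOVA significant. Time since RV306 is only a partial proxy for stage. Titers at single visits are not baseline-corrected.

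A reader might also infer stronger points that the documents do not support:

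- **That every vaccine-versus-placebo contrast is biased.** All active versus placebo is not, at the target 4:1 allocation in each stage.
- **That the trial faces 10 to 24% type I error.** Those rates belong to an ungated 5% t-test, which the SAP does not plan for these pairs.
- **That the placebo split is badly unequal**, because SAP 4.4.2 says "a new set of assignments was generated for Groups 3 and 4 based on the updated allocation ratios". The same section says that Groups 1 and 2 were stopped so as to keep approximately the new sizes, which points to about 8 + 8. Only the achieved numbers are missing.
- **That the SAP departs from the protocol or misdescribes the design.** The protocol pools as well, and each stage does have its own randomised placebos. The loss of concurrency arises in the analysis.

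**Conclusion.** The concern holds for the individual vaccine-versus-placebo contrasts, the five-group ANOVA and the displayed placebo rates. By target, 50% of each comparator is non-concurrent, and a stage shift of d SD biases each contrast by d/2, with opposite signs in the two stages. At d = 0.5 the planned procedure gives a false-positive rate of about 0.4% to 1.6% per pair, roughly four times its rate with no shift but still low. For all active versus placebo there is no bias, only a conservative test with lower power: about 2.9% type I error and about 73% power at 0.79 SD when d = 1.

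These results assume 8 + 8 placebo recipients, normal log titers with equal variance and a constant stage shift. The values of d are illustrative. Not concurrent here refers to enrolment and vaccination dates; the 12-month follow-up periods may overlap. The practical weight is moderate and the remedy is cheap. The ALFQ contrast, which coincides with stage, is a separate matter.

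**What to change.** 1. Stratify the all-active-versus-placebo test by enrolment stage, for example with a model containing active/placebo and stage. At the target allocation the SE is 0.28 SD either way, so this costs one degree of freedom.
2. Show placebo by stage (with Groups 1+2; with Groups 3+4) beside the pooled column in the main safety and titer tables, such as SAP Tables 13, 16, 22, 32 and 37.
3. Prespecify a within-stage contrast of each vaccine group with its own stage's placebo as a supportive analysis, and keep the pooled pairwise test as planned.
4. Report the achieved vaccine and placebo numbers per stage, and state the allocation ratio used in each stage, so that SAP 4.1 and 4.4.2 read consistently.

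A stage term should not be added to the five-group ANOVA as the main test, because it also inflates the standard errors of the ALFQ pairwise comparisons (0.354 to 0.612 SD for Group 1 versus Group 3).

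The cost is some SAP wording, extra table columns and one set of supportive contrasts. The 8-person placebo columns will have wide intervals (zero-event upper limit 36.9% against 20.6%), and the supportive contrasts detect 1.27 SD rather than 1.02 SD at 80% power. They should be read as a check on the pooled result.
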